This statistical analysis plan (SAP) describes detailed aspects of data preparation and analysis according to the guidelines for the content of statistical analysis plans in clinical trial (1) and was written before starting the final analysis. The SAP is based on the final trial protocol version 1.5_10-07-2024 and the study protocol article: [name], [name], [name], Trøstrup J, Bieler T, [name], [name]. To allow or avoid pain during shoulder rehabilitation exercises for patients with chronic rotator cuff tendinopathy-Study protocol for a randomized controlled trial (the PASE trial). *Trials*. 2024 Feb 21;25(1):135. doi: 10.1186/s13063-024-07973-6. PMID: 38383459; PMCID: PMC10880378 (2).

2. Study synopsis

Introduction

Shoulder disorders are the third most common musculoskeletal disorder with a lifetime prevalence of up to 70% in the general population (3, 4). Rotator cuff (RC) tendinopathy is the most reported shoulder disorder in the general population with highest prevalence in overhead athletes and adult working-age population (5, 6). A growing body of evidence support exercise therapy as an effective intervention, but to date there are no prospective randomized controlled trials addressing pain as an intervention variable (7, 8). For more details about the background and rationale see the protocol article (2).

Objectives

The primary purpose of this project is to examine the effect of allowing pain versus avoiding pain during shoulder exercises for patients with symptomatic chronic RC tendinopathy measured on patient-reported pain and disability and objective outcomes.

Hypothesis

We hypothesize that allowing pain during exercises will result in a better outcome measured on Shoulder Pain And Disability Index (SPADI) (the primary outcome) compared to avoiding pain in patients with RC tendinopathy.

3. Study methods

STATISTICAL ANALYSIS PLAN PASE TRIAL

Trial design

This is a single-site, prospective, outcome assessor blinded, pragmatic, randomized, controlled, superiority trial with a two-group parallel design, comparing a pain allowance program (PAllow) with a pain avoidance program (PAvoid). Patients are randomized equally (1:1) to receive either PAllow or PAvoid. The study has two phases; a main trial phase lasting 26 weeks, which corresponds to the planned duration of the individualized rehabilitation program, and a follow-up phase lasting an additional 26 weeks.

Randomization

Participants are randomly assigned to either PAllow or PAvoid with a 1:1 allocation ratio.. To counter potential imbalance in the randomization both stratification and blocking are employed. Stratification by including department (department of sports medicine/ department of occupational medicine) is necessary because of possible differences in clinical practices furthermore stratification by sex and age (± 35 years) are employed. The allocation sequence is computer-generated with permuted random blocks, set up by a data manager outside the project.

Sample size

The sample size is calculated to test the superiority of PAllow over PAvoid based on the change in the SPADI (primary outcome) from baseline to week 26 (primary endpoint). We aim at having a power of 80% to verify an effect equal to or higher than the Minimal Clinical Important Difference (MCID) of 10 points on SPADI at a 5% significance level. A total of 35 patients are required per group to establish this mean difference of 10 points with a common standard deviation of 15 (0–100 scale). To account for dropouts (max 20%), we are planning to include a total of 42 per group (2).

Intervention and datacollection

For both groups the intervention period lasts 26 weeks. During that period, participants in both groups are offered 8 individual on-site sessions with an assigned sports physiotherapist. Additionally, participants have a home exercise program. Two exercise programs were developed with the principal difference being allowing or avoiding pain during the exercises. Data are collected on three occasions at the hospital; at baseline before randomization and to times after; at 26 weeks (post intervention/primary endpoint), and at 1-year (follow-up/secondary endpoint).

4. Statistical analysis plan

Study Population definitions

Intention-to-treat (ITT)

The primary efficacy analysis performed is assessment of the between-group difference in change in the SPADI score after 26 weeks in the ITT population. ITT population is defined as all randomized participants irrespective of compliance or withdrawals. A patient will be considered randomized as soon as intervention/training group is assigned by according to the allocation sequence.

As-observed population (AO)

The AO population is defined as participants who have the outcome of interest assessed at a given time point of interest (i.e. no imputation of missing data), primarily used for demographics presentation.

Per-protocol population (PP)

The per-protocol (PP) population is defined as participants who adhere to this protocol, defined by the following criteria in both groups:

- Are included in the AO population, and
- have attended at least 75 % of the scheduled on-site physiotherapist appointments, and
- have 75% compliance to pain perception during exercises (documented by pain diary), and
- have a minimum of 6 home-based training sessions weekly for the first 16 weeks of the 26 weeks intervention (documented by the exercise logbook), and
- do not engage in concomitant supervised exercise-based treatment for the shoulder and do not receive new, important interventions (e.g., no surgery, no shock-wave therapy or cortico-steroid injection) in the main trial phase

Primary analysis

The mean SPADI at each of the study time points, which includes the primary outcome SPADI at week 26, will be analyzed for each of the randomization groups in linear regression models; the models will be parameterized such that they directly produce inference on the difference between

STATISTICAL ANALYSIS PLAN PASE TRIAL

the randomization groups at each of the follow-up time points, beyond the difference that may be present at baseline. The analyses will account for repeated measurement by means of Generalized Estimating Equations (GEE).

Secondary outcome analysis

Secondary outcomes will be analysed similar to the primary outcome, in linear regression models with GEE.

Missing data

The presence of missing data at the various study time points is modelled by logistic regression models using age, sex, clinic, group allocation (masked) and baseline value as explanatory variables. Estimated probabilities for the data being not missing from these models will be used in inverse probability weights (IPW) to account for possible differential attrition; GEE adjusts inference to account for these weights (2, 9).

General statistical approach

Summary tables for quantitative variables included in publication are expected to include at least mean and standard deviation (SD) by treatment group. All summary tables for qualitative variables will display counts and percentages by treatment group. Baseline data are defined as the all measurements performed at the baseline visit.

An alpha level of 0.05 (two-sided) will be considered statistically significant. All data analysis will be carried out according to the pre-established analysis plan by a statistician who is blinded to the allocated interventions for the analysis. Data analysis is performed in SAS version 9.4 and R version 4.3.1.

5. Timing and implementation of analysis

The analysis of both primary and secondary outcome will be performed at the same time.

The implementation procedure of the SAP for the PASE trial:

- An otherwised not involved research secretary will export the blinded data from the REDCAP Research Database
- The treatment arms will be coded into “A” and “B” thus leaving all others blinded to treatment allocation during analysis

STATISTICAL ANALYSIS PLAN PASE TRIAL

[figure not shown]
- Blinded data will be delivered to VS according to the statistical model requirements
- All analyses will be conducted blinded from allocation to any of the two treatment arms by an external statistician (VS). Before unblinding a consensus document will be described and signed by all authors of the study.

6. Figure legends

[figure not shown]
Figure 1: Flow of participants throughout the study

Figure 2: SPADI at baseline, week 26 and week 52. The graphs illustrate the results from the Intention-To-Treat population with datapoints representing means and error bars indicate 95% CI's. PAllow, allowing pain group; PAvoid, avoiding pain group; SPADI, Shoulder Pain and Disability Index

STATISTICAL ANALYSIS PLAN PASE TRIAL

STATISTICAL ANALYSIS PLAN PASE TRIAL

(This particular figure is made as an example and based on fantasy data)

STATISTICAL ANALYSIS PLAN PASE TRIAL

Table 1 Demographics and Baseline Data for PAallow and PAvoid group^a

Characteristics	PAallow Group (n=xx)	PAvoid Group (n=xx)
Age in years		
Male		
Height in cm		
Weight in kg		
BMI in kg/m ²		
Dominant side affected		
Symptom duration in months		
Smoking		
- Never		
- Not anymore		
- Yes		
Pain medication past 4 weeks		
- 1-4 times a day		
- 2-6 times a week		
- 1-4 times a month		
Less than once a month or never		
Work		
Shoulder demanding job (y/n)		
Working status		
- working full-time/part-time		
- Partially on sick leave		
- Not working		
Sport participation		
- Elite		
- Recreational		
- No		
Primary outcome measure		
SPADI (0-100; 100 = most disabled)		
Secondary self-reported outcomes		
Quick DASH (0-100; 100 = most disabled)		
Quick DASH Work ^c		
Quick DASH Sport ^d		
Pain in NPRS (0-10); 10 = most pain		
- Pain at rest ^b		
- Pain during daily activity ^b		
- Worst pain past 24 hours ^b		
- Pain at night ^b		
- Pain acceptance during training ^b		
Work Ability Index		

^a Data are reported as mean \pm SD or n (%) unless otherwise indicated.

PAallow, allowing pain; PAvoid, avoiding pain; BMI, Body Mass Index; SPADI, Shoulder Pain and Disability Index; Quick DASH, Disability Arm Shoulder Hand short form; SD, Standard Deviation

^b All pain is measured using Numeric Pain Rating Scale (NPRS)

^c Optional module (answered if working)

^d Optional module (answered if sport participation)

STATISTICAL ANALYSIS PLAN PASE TRIAL

Table 2 Changes From Baseline to 26 and 52 weeks follow-up for primary and secondary outcome (Intention-to-Treat population)								
	From baseline to 26 weeks				From baseline to 52 weeks			
	Within group change ^{a)}		Adjusted ^{a)}		Within group change ^{a)}		Adjusted ^{a)}	
	PAllow (n=x) Change (SE)	PAvoid (n=x) Change (SE)	Between-Group difference on change (95% CI)	p-value	PAllow (n=x) Change (SE)	PAvoid (n=x) Change (SE)	Between-Group difference on change (95% CI)	p-value
Primary Outcome SPADI								
Secondary Outcomes Quick DASH Quick DASH Work ^c Quick DASH Sport ^d								
Pain in NPRS - Pain at rest - Pain during daily activity - Worst pain past 24 hours - Pain at night - Pain acceptance during training								
Work Ability Index								
GRS								
ROM (°) Scaption passive Scaption active External rotation passive External rotation active								
Strength (MVC) (Nm) Scaption External rotation								
Pressure Pain Threshold (kPa)								

STATISTICAL ANALYSIS PLAN PASE TRIAL

^a Adjusted for age, sex and clinic.

PAllow, allowing pain; PAvoid, avoiding pain; SPADI, Shoulder Pain and Disability Index; Quick DASH, Disability Arm Shoulder Hand short form; SE, Standard Error; 95%CI, 95% Confidence Intervals; NPRS, Numeric Pain Rating Scale; GRS, Global Rating Scale; $^\circ$, degrees; MVC, Maximum isometric voluntary contraction; kPa, kilo Pascal

^c Optional module (answered if working)

^d Optional module (answered if sport participation)

STATISTICAL ANALYSIS PLAN PASE TRIAL

Corresponding table is made for the Per Protocol population for supplementary file

Table 3 Changes From Baseline to 26 and 52 weeks follow-up for primary and secondary outcome (Intention-to-Treat population)								
	From baseline to 26 weeks				From baseline to 52 weeks			
	Within group change ^{a)}	Adjusted ^{a)}	Between-Group difference on change (95% CI)	p-value	Within group change ^{a)}	Adjusted ^{a)}	Between-Group difference on change (95% CI)	p-value
Primary Outcome SPADI								
Secondary Outcomes Quick DASH Quick DASH Work ^c Quick DASH Sport ^d								
Pain in NPRS - Pain at rest - Pain during daily activity - Worst pain past 24 hours - Pain at night - Pain acceptance during training								
Work Ability Index								
GRS								
ROM (°) Scaption passive Scaption active External rotation passive External rotation active								
Strength (MVC) (Nm) Scaption External rotation								
Pressure Pain Threshold (kPa)								

STATISTICAL ANALYSIS PLAN PASE TRIAL

^a Adjusted for age, sex and clinic.

PAllow, allowing pain; PAvoid, avoiding pain; SPADI, Shoulder Pain and Disability Index; Quick DASH, Disability Arm Shoulder Hand short form; SE, Standard Error; 95%CI, 95% Confidence Intervals; NPRS, Numeric Pain Rating Scale; GRS, Global Rating Scale; $^{\circ}$, degrees; MVC, Maximum isometric voluntary contraction; kPa, kilo Pascal

^c Optional module (answered if working)

^d Optional module (answered if sport participation)

7. References

2. [name], [name], [name], Trostrup J, Bieler T, [name], et al. To allow or avoid pain during shoulder rehabilitation exercises for patients with chronic rotator cuff tendinopathy-Study protocol for a randomized controlled trial (the PASE trial). *Trials*. 2024;25(1):135.
4. Lucas J, van Doorn P, Hegedus E, Lewis J, van der Windt D. A systematic review of the global prevalence and incidence of shoulder pain. *BMC musculoskeletal disorders*. 2022;23(1):1073.
5. [name], Johansson FR, Borms D, Maenhout A. Prevention of shoulder injuries in overhead athletes: a science-based approach. *Braz J Phys Ther*. 2015;0.

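### 42 patients per group preserve the required 35 only up to 16.7% dropout, not the stated maximum of 20%

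*SAP*

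**What the plan says.** The Sample size paragraph in section 3 of the SAP gives the inputs: "We aim at having a power of 80"%, a difference equal to the "Minimal Clinical Important Difference (MCID) of 10 points on SPADI", and a test "at a 5% significance level". Sidedness is fixed in section 4, General statistical approach: "An alpha level of 0.05 (two-sided) will be considered statistically significant".

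From these the SAP concludes: "A total of 35 patients are required per group to establish this mean difference of 10 points with a common standard deviation of 15". The next sentence turns that requirement into an enrolment target: "To account for dropouts (max 20%), we are planning to include a total of 42 per group (2" (the final 2 is a literature reference). No inflation formula is given, and the SAP does not say whether the 20% is a share of patients enrolled or of patients required.

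**The concern.** Dropouts come from the patients who were randomized. A dropout ceiling of 20%, stated next to an enrolment number, is therefore naturally read as 20% of the 42. On that reading the enrolment target should still leave 35 per group once the ceiling is reached, and it does not.

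Readers use the sample-size statement to judge how informative a null result is. If observed dropout falls between 16.7% and 20%, this SAP would lead them to believe that the required number had been secured when it had not.

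**Working it through.** **Inputs (all from the SAP).** Difference 10 SPADI points; SD 15; power 80%; two-sided alpha 5%; 1:1 allocation; 35 required per group; 42 planned per group; dropout at most 20%.

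**1. The base figure.** For two means, n per group = 2 × (1.960 + 0.842)² × (15/10)² = 35.3. The stated 35 is this value rounded down. A one-sided test would give 28 to 29 and does not fit, so the calculation is two-sided. The 35 is accepted here as the plan's own requirement.

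**2. The inflation step.**

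- Adding 20% to the requirement: 35 × 1.20 = 42. This reproduces the plan's figure exactly.
- Allowing for a 20% loss among those enrolled: 35 / (1 − 0.20) = 43.75, so 44 per group and 88 in total. Check: 44 × 0.80 = 35.2.

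**3. What 42 per group delivers.**

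- At 20% dropout: 42 × 0.20 = 8.4 lost, 33.6 left. In total, 84 × 0.80 = 67.2 left, against 2 × 35 = 70.
- Largest loss that still leaves 35: 42 − 35 = 7, and 7/42 = 16.7%.

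**4. Consequence for power.** Normal approximation: power = Φ(10 / (15 × √(2/n)) − 1.960). The second figure in each row is from the two-sample t-test.

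| Dropout from 42 | n per group | Power, normal | Power, t |
|---|---|---|---|
| 0% | 42 | 86.3% | 85.5% |
| 10% | 37.8 | 82.6% | 81.6% |
| 16.7% | 35 | 79.6% | 78.5% |
| 19.0% (8 patients) | 34 | 78.5% | 77.3% |
| 20% | 33.6 | 78.0% | 76.8% |

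The inflation step therefore costs 79.6 − 78.0 = 1.6 points (normal) or 78.5 − 76.8 = 1.7 points (t) at the ceiling.

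**5. Consequence for the detectable difference.** At 80% power it is 2.802 × 15 × √(2/n): 10.05 points with 35 per group and 10.25 points with 33.6.

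**The case against.** **Whole patients.** Patients are not fractional and 20% is a maximum. Within a group of 42, at most 8 can be lost without exceeding it (8/42 = 19.0%; 9/42 = 21.4%). That leaves 34, one short of 35, and the power cost is about 1.1 to 1.2 points. On the same count 43 per group would suffice, since 43 − 8 = 35. This is fair if the ceiling is applied to each group separately. Applied to the whole trial it allows 16 losses of 84, leaving 68 against 70, and an uneven split of 9 and 7 leaves 33 in one group. Either way the stated 35 is not kept.

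**Where 80% power is lost.** With 35 per group the power is already 79.6% (normal) or 78.5% (t). Strictly, 80% is lost a little before 16.7% dropout: at 1 − 35.3/42 = 15.9% by the normal formula, or 1 − 36.3/42 = 13.6% using the t-test's 36.3. This is correct. The 16.7% marks where the plan's own count of 35 fails, and part of the gap between 80% and the power at 20% dropout comes from rounding 35.3 down, not from the inflation step.

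**Another base for the 20%.** The sentence may have meant 20% of the 35 required. The SAP does not say so, and anyone checking the claim will compare it with dropout among the randomized. Rounding is no explanation either, because 43.75 does not round to 42.

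**The planned analysis is not a t-test.** The primary analysis is a GEE model with inverse probability weights in the intention-to-treat population, and Table 2 reports differences adjusted for age, sex and clinic. Completer power is only a rough guide to its precision. That limits the power figures but not the count: weighting addresses differential attrition and does not restore missing week-26 outcomes.

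**Conclusion.** The point holds and is minor. The SAP's 35 required, 42 enrolled and 20% maximum dropout cannot all be true. At the ceiling, 33.6 per group remain on average, 1.4 short. Measured at enrolment, the plan is 2 per group short (42 against 44; 84 against 88 in total). In unadjusted planning power the loss relative to 35 per group is 1.6 to 1.7 points, or a little over 1 point if exactly 34 remain in each group.

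This rests on reading the 20% as a share of those enrolled, on taking 35 as the requirement, and on an unadjusted two-group comparison of completers. The power of the weighted GEE was not computed because the SAP gives no within-patient correlation. Up to 16.7% dropout the plan meets its own requirement of 35.

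**What to change.** Replace the last sentence of the Sample size paragraph with a statement of what 42 per group covers, for example:

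> With 42 per group, the required 35 per group remain evaluable at week 26 if dropout is at most 16.7% (7 per group). At 20% dropout about 33–34 per group remain, and the unadjusted planning power for a 10-point difference with SD 15 is about 77–78%.

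The 77–78% corresponds to the expected 33.6 per group (76.8% by the t-test, 78.0% by the normal formula).

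The cost is one sentence and a slightly less favourable statement of protection against dropout. No patients are added and the analysis does not change. Raising enrolment to 44 per group is not requested: the SAP was written shortly ahead of the final analysis, and the shortfall is too small to warrant it.

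### The primary SPADI contrast is a difference in change without baseline SPADI as a covariate: valid, but usually less precise than the data already collected allow

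*SAP*

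**What the plan says.** In section 4, the intention-to-treat paragraph makes the primary analysis the "between-group difference in change in the SPADI score after 26 weeks". The Primary analysis paragraph models "The mean SPADI at each of the study time points, which includes the primary outcome SPADI at week 26" by linear regression with GEE. The effect is the difference between "the randomization groups at each of the follow-up time points, beyond the difference that may be present at baseline". Baseline SPADI is therefore one of the outcomes, and the effect is the group-by-time term.

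Footnote a of Table 2 describes the reported contrast as "Adjusted for age, sex and clinic". Baseline SPADI is not listed. It is an explanatory variable only in the Missing data paragraph, where the weight model uses "age, sex, clinic, group allocation (masked) and baseline value as explanatory variables".

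The Sample size paragraph in section 3 is likewise "based on the change in the SPADI (primary outcome) from baseline to week 26". It assumes a 10-point difference and an SD of 15, and arrives at 35 evaluable patients per group.

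**The concern.** Subtracting the baseline value fixes the slope of follow-up on baseline at 1. The slope in the data is usually below 1, and the change contrast then over-corrects for baseline. This adds variance and leaves the result of a single trial sensitive to chance baseline imbalance. Estimating the slope removes both problems in large samples, using a measurement taken before randomisation.

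Two details make it worse. The SAP does not say how age, sex and clinic enter the model. If they enter as main effects only, they contribute nothing to a within-patient contrast when data are complete, and a reader may take the *Adjusted* column to mean more than it does. The SAP also names no working correlation, and with dropout the precision of the planned contrast depends on it.

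At stake is the width of the week 26 confidence interval in a trial with little spare power, not the validity of the test.

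**Working it through.** **Inputs from the SAP.** Difference 10; SD 15; two-sided alpha 0.05; power 80%; 35 per group evaluable; 42 per group randomised; dropout at most 20%. **Assumed, because the SAP does not give them:** rho, the baseline/follow-up correlation, and k = follow-up SD / baseline SD.

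**The plan's own figure.** n = 2 × (15 × (1.960 + 0.842) / 10)² = 35.3 per group. The stated 35 is reproduced to within rounding. Power at 35 per group is 79.6% (normal) or 78.5% (t test).

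**Large-sample comparison.** With baseline SD set to 1:
- variance of the change contrast ∝ k² + 1 − 2·rho·k
- variance of the baseline-adjusted contrast ∝ k²(1 − rho²)
- penalty = (1 − rho·k)² / (k²(1 − rho²))

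The penalty is never negative and is zero only when rho·k = 1. For example, at k = 1 and rho = 0.5 it is 0.25 / 0.75 = 33%.

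| k | rho 0.3 | rho 0.5 | rho 0.7 | rho 0.9 |
|---|---|---|---|---|
| 0.8 | 99% | 75% | 59% | 64% |
| 1 | 54% | 33% | 18% | 5% |
| 1.25 | 27% | 12% | 2% | 5% |
| 1.5 | 15% | 4% | 0.2% | 29% |

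**Power at 35 per group** (t test, covariate degrees of freedom ignored). If 15 is the SD of change, the effective SD after adjustment is 15 / √(1 + penalty). At k = 1 this is 12.1, 13.0, 13.8 and 14.6 for the four correlations, giving power of 93%, 89%, 85% and 81% against 78.5% for the change contrast. At rho 0.5, adjusted power is 83% for k = 1.25 and 80% for k = 1.5.

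The SAP does not say whether 15 is the SD of change or of the raw score. If it is the raw score and k = 1, change against adjusted power is 64% vs 82% (rho 0.3), 79% vs 89% (0.5) and 94% vs 97% (0.7).

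**Chance imbalance.** At k = 1, a baseline difference of 5 points shifts the change contrast by 5 × (1 − rho) = 3.5, 2.5, 1.5 and 0.5 points. The shift averages zero over randomisations. It is the same penalty seen within one trial, not a second one.

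**Does GEE or the covariate list bring in baseline adjustment?** No. On a simulated complete data set of 70 patients, the group-by-time term with age, sex and clinic as main effects was −7.542 under both independence and exchangeable working correlation. The raw difference in mean change was also −7.542.

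**Simulation.** 2000 trials per setting, 84 patients, stratified blocks, change SD 15, k = 1. Entries are empirical SEs, change vs baseline-adjusted.

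| Setting | rho 0.3 | rho 0.5 | rho 0.7 | rho 0.9 |
|---|---|---|---|---|
| Complete data | 3.31 vs 2.61 | 3.30 vs 2.81 | 3.28 vs 2.99 | 3.25 vs 3.16 |
| About 20% missing, plan's weights, exchangeable | 3.67 vs 3.15 | 3.71 vs 3.38 | 3.76 vs 3.64 | 3.88 vs 4.10 |
| Same, independence | 3.71 vs 3.16 | 3.84 vs 3.40 | 4.18 vs 3.65 | 6.03 vs 3.92 |

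With dropout, exchangeable correlation, rho 0.5 and k = 1.5, the SEs are 3.81 vs 3.81. Adding age, sex and clinic to the weighted change model moved the estimate by a median of 0.14 to 0.22 points (exchangeable) or 0.29 to 0.89 points (independence).

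A separate weighted simulation with about 20% dropout and exchangeable correlation gave 3.56 vs 3.03, 3.47 vs 3.05 and 3.58 vs 3.37 at rho 0.3, 0.5 and 0.7.

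**The case against.** The strongest reply is that nothing here is wrong. Sample size, primary analysis, model and table heading all refer to change; the contrast is prespecified, unbiased and validly tested. That stands, and it is why the point concerns precision only.

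The size of the gain is assumed. This also stands: the penalty runs from 99% to 0.2% over the range examined, and with dropout there are settings with no gain (rho 0.5, k = 1.5) or a small loss (rho 0.9, exchangeable). The rho 0.9 column deserves little weight either way. With change SD 15 and k = 1 it implies a raw SD of 15 / √0.2 = 33.5 on a 0–100 scale. That discounts both the 6.03 under independence and the 4.10 under exchangeable correlation.

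The remark on the *Adjusted* column is conditional. It requires main effects only, which the SAP does not state, and under dropout with independence the covariates can move the estimate by up to 0.89 points in the median. It is fair as a gap in specification, not as a proven emptiness.

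Finally, the change comes late. It replaces the primary estimator of a SAP that rests on a protocol and a protocol article not shown here, and patients without follow-up are then represented only through the weights. This is a reason to record the change formally while the analysis is blinded. It does not remove the case for making it.

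**Conclusion.** The point holds as a recommended improvement, not a defect. The plan's test is valid: the contrast is unbiased under randomisation and, with missing data, if the weight model is right. In large samples the baseline-adjusted contrast is never less precise. With equal SDs and a correlation of 0.3 to 0.7, the planned contrast carries 18% to 54% more variance. If 15 is the SD of change, adjustment raises power at 35 per group from 78.5% to between 85% and 93%. If follow-up scores are more variable than baseline scores, the gain may be small or nil.

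The gain would be useful here. At 20% dropout, 42 × 0.8 = 33.6 per group remain, where power is 76.8% for change and 87.5% adjusted (rho 0.5, k = 1, SD of change 15).

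The direction is secure in large samples. The size rests on a correlation and an SD ratio that the SAP does not give.

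**What to change.** Amend the primary analysis before unblinding, preferably before the blinded analysis starts:

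- Use SPADI at weeks 26 and 52 as the GEE outcomes, with group, time, group-by-time, baseline SPADI, baseline-by-time, department, sex and age as covariates.
- Report the adjusted group difference at week 26 as primary.
- Treat secondary outcomes that have a baseline value in the same way.
- Name the working correlation.
- Keep within-group changes and Figure 2 as descriptive.

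A model that constrains the baseline means to be equal is an alternative only with a working correlation that links baseline to follow-up. Under independence it discards baseline: with complete data and rho 0.7 (400 simulated trials) its SE was 4.11, against 3.30 for the planned contrast and 3.09 with the baseline covariate.

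The cost is SAP wording and a few lines of code. No new data are needed, and the estimand is unchanged under randomisation. The within-group columns of Table 2 become descriptive. Because the SAP rests on the protocol and the protocol article, the change should be a dated, documented amendment. Section 5 already requires a signed document at a suitable stage ("Before unblinding a consensus document will be described and signed by all authors of the study"), but the amendment should come before that step.

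### Does applying the primary change-from-baseline weighted GEE to every secondary outcome break down for GRS and the QuickDASH Work and Sport modules?

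*SAP*

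**What the plan says.** Section 4 of the SAP, under Secondary outcome analysis, has one sentence on the model: "Secondary outcomes will be analysed similar to the primary outcome, in linear regression models with GEE". The primary model it refers to is set up to give the difference between "the randomization groups at each of the follow-up time points, beyond the difference that may be present at baseline". Under Missing data, the chance of a value being present is modelled "using age, sex, clinic, group allocation (masked) and baseline value as explanatory variables", and the fitted probabilities "will be used in inverse probability weights (IPW) to account for possible differential attrition".

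Table 2 is titled "Changes From Baseline to 26 and 52 weeks follow-up for primary and secondary outcome (Intention-to-Treat population" and has rows for GRS, QuickDASH Work and QuickDASH Sport. A footnote to the Work row reads "Optional module (answered if working"; a parallel footnote limits the Sport row to those who take part in sport. For GRS the SAP gives only the expansion of the abbreviation, "GRS, Global Rating Scale". Table 1 has a block headed "Secondary self-reported outcomes" with QuickDASH and its two modules, five pain items and the Work Ability Index. GRS is not in it.

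**The concern.** Two things look wrong.

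- **GRS.** If GRS is recorded only after treatment, there is no baseline difference to remove and no baseline value for the weight model. The Table 2 row could not then be produced exactly as described.
- **Work and Sport modules.** A blank score can mean that the person left the study or that the module did not apply. The SAP does not separate the two, so a person who stops working could be handled as lost to follow-up and represented by people still working. Whether someone works or does sport at week 26 may itself depend on treatment. The row would then compare groups partly selected after randomisation, under an intention-to-treat title. An arm that keeps more symptomatic patients at work could look worse on the Work module for that reason alone.

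At stake is the reading of three secondary rows.

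**Working it through.** **Plan's own figure.** The SAP gives no number for these outcomes. Its one calculation is for SPADI: 2 × (15 × (1.960 + 0.842) / 10)² = 35.3 per group, close to the stated 35. Nothing below touches it.

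**How many rows are affected.** Table 2 lists QuickDASH 3 + pain 5 + Work Ability Index 1 + GRS 1 + range of motion 4 + strength 2 + pressure pain threshold 1 = 17 secondary outcomes. Over two follow-up visits that is 34 comparisons. GRS accounts for 2 and the two modules for 4.

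**GRS: is a baseline absent?** Absence from Table 1 does not settle it. Range of motion, strength and pressure pain threshold (7 rows) are also in Table 2 and not in Table 1, and nobody would infer that they have no baseline. Table 1's block is for self-reported outcomes, which makes GRS the odd one out, but the SAP does not say how GRS is obtained. Section 3 describes data collection at baseline, week 26 and one year without excepting any measure.

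**GRS: what if there is none?** The natural model has six parameters: intercept, group, week 26, week 52 and the two group-by-visit terms. Three visits in two groups give 6 cell means, so the design has rank 6 of 6. Without baseline there are 2 × 2 = 4 cell means and rank 4 of 6. The contrast relative to baseline is then not identified, but the plain group differences at weeks 26 and 52 are. Under randomisation the expected baseline difference is zero, so these answer the same question. The weight model keeps age, sex, clinic and group.

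**Modules: who is weighted?** The weight model uses the outcome's baseline value as a covariate. A person not working at baseline has no Work score, so drops out of that model and receives no weight, even with a later score. Workers are therefore not up-weighted to stand for people who never answered. The open group is those who answer at baseline but not at follow-up.

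**Modules: is there bias?** A large-sample simulation with no true effect on a 0–100 scale, with weights from age, group and baseline value where follow-up answering varied (all inputs assumed), gave:

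| How follow-up answering arises | Spurious difference |
|---|---|
| Fixed by baseline work status | about 0 |
| Depends on the outcome, equally in both arms | about 0 |
| Depends on the outcome, differently by arm | about −1.3 points |

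**Modules: would another rule do better?** Take 80% versus 70% working at week 26, with the least disabled working (assumed). The mean of a standard normal variable truncated to its lowest fraction p is −φ(a)/p, where a is the p-quantile. This gives −0.350 at p = 0.80 and −0.497 at p = 0.70, a difference of 0.147 SD. With a correlation of 0.5 to 1.0 between work status and disability, the spurious difference is 0.07 to 0.15 SD, or 1.5 to 3 points if the SD is 20 (assumed).

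Three analyses of this scenario were simulated, with a baseline to follow-up correlation of 0.3 to 0.7 (assumed):

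| Analysis | Spurious difference (SD) |
|---|---|
| Baseline responders, weights only for true loss to follow-up | 0.07 to 0.15 |
| SAP weighting on group and baseline value | 0.04 to 0.14 |
| Change only in those with both scores, unweighted | 0.02 to 0.11 |

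The planned weighting does slightly better than the obvious restriction. The complete-case version does somewhat better here, but no option removes the bias.

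**The case for a change.** The strongest opposing case is that the modules need no inference. The footnotes show that some randomised patients may have no score by design, and Table 1 itself has categories for not working and for no sport, yet the rows sit under an intention-to-treat title. One recruiting department is occupational medicine, so a difference in return to work between arms is plausible. For GRS, silence on whether a baseline exists is itself a gap, and a follow-up-only model is not the one written down. Clarifying wording would cost almost nothing.

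Most of this stands as description. The SAP does not say whether GRS has a baseline, has no rule for scores that do not apply, and gives no row-level numbers for the modules. It does not stand as a reason to alter the analysis. The rule asks for a similar analysis, not an identical one, so reporting follow-up differences for GRS lies within it. The footnotes on the module rows already tell the reader who contributes. The selection problem comes from who can answer at follow-up, and restricting to baseline responders does not reliably remove it.

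**Conclusion.** No change to the plan follows. The blanket rule is loose for 3 of 17 secondary outcomes, but the gaps are ones an analyst fills sensibly: a direct group comparison for GRS if it has no baseline, and a module comparison that in practice rests on people with a baseline module score. The claim that GRS cannot be analysed depends on a missing baseline that the SAP does not state. The claim of bias in the module rows depends on follow-up work or sport status being related to outcome differently in the two arms. Under the assumed 80% versus 70% scenario, that bias is about 0.04 to 0.14 SD with the planned weights, or 0.8 to 2.8 points at an assumed SD of 20. The restriction to baseline responders leaves 0.07 to 0.15 SD. The module rows should be read with care because follow-up status arises after randomisation, but a reader can see that from the footnotes. SPADI, the primary outcome, is not affected.
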